2 BACKGROUND AND SIGNIFICANCE

[figure not shown]
Diabetic enteropathy

The term diabetic *enteropathy* implies that diabetes mellitus (DM) can affect the entire gastrointestinal (GI) tract¹. Diabetic enteropathy may be asymptomatic or manifest with upper (i.e., heartburn, dysphagia, dyspepsia, gastroparesis) or lower GI symptoms (diarrhea, constipation, and fecal incontinence). Gastrointestinal dysmotility in DM is multifactorial: extrinsic and intrinsic (i.e., enteric) neural dysfunction, hyperglycemia, and hormonal disturbances have been implicated.

Patients with DM may have accelerated or delayed gastric emptying (GE), increased and reduced gastric sensation, and impaired gastric accommodation. Antral hypomotility and/or pylorospasm, which can result from a vagal neuropathy, can delay GE²¹. Much attention has focused on delayed gastric emptying or gastroparesis as an explanation for upper GI symptoms in DM. Similar to idiopathic gastroparesis, the contribution of delayed gastric emptying to symptoms in patients with DM gastroparesis is unclear for several reasons. A majority of patients report symptoms within 1 hour of eating. However, even normally, only approximately 25% of solids have emptied from the stomach by then. Hence, delayed gastric emptying is unlikely to explain early postprandial symptoms. Second, a majority of patients with DM and delayed gastric emptying are asymptomatic. Third, a substantial proportion of DM patients with GI symptoms who underwent scintigraphy, i.e., 55 of 129 patients (42%) in our cohort, had normal gastric emptying; the remainder had delayed (36%) or rapid GE (22%)⁴. Symptoms did not predict abnormal (i.e., delayed or rapid) gastric emptying in patients with DM and GI symptoms⁴. Even in functional dyspepsia, gastric emptying and accommodation only explained one-third of the variance in postprandial symptoms^{22,23}.

Impaired gastric accommodation and increased gastric sensation have been implicated to cause early satiety in functional dyspepsia²⁴. Our understanding of gastric accommodation and gastric sensation in DM is limited to 3 studies, which assessed a total of 37 patients. While gastric sensation was increased in both studies, gastric compliance in DM was increased in 1 study⁵ and reduced in 2 studies^{6,25}. Another study, with 10 healthy subjects and 10 DM patients, observed an association between a lack of symptoms in diabetic gastrointestinal motility disorders and visceral afferent neuropathy identified by esophageal electrical stimulation²⁶. Thus, while sensory disturbances – increased or decreased – are recognized in diabetic peripheral neuropathy, there are minimal data on GI sensation. Conceivably, GI sensory disturbances influence the expression of GI motor dysfunctions in DM. For example, asymptomatic delayed gastric emptying may be explained by vagal neuropathy. Conversely, in symptomatic patients, delayed gastric emptying is likely explained by enteric dysfunction rather than vagal neuropathy.

Figure 1. Gastrointestinal symptoms during enteral nutrient infusion. A higher proportion of patients with functional dyspepsia (n=25) than controls (n=33) reported symptoms of moderate severity or worse during enteral carbohydrate ($p \leq 0.01$) and lipid ($p \leq 0.01$) infusions.

studies have evaluated the effects of duodenal nutrient infusion on glycemia, hormonal responses, glucose absorption, and gastroduodenal motility but not sensation in DM²⁸⁻³¹. Moreover, no studies have integrated findings from assessments of gastric emptying, accommodation, and sensation. This is a major limitation since the expression (symptoms) resulting from a disturbance may depend on other coexisting disturbances. For example, it is conceivable that intestinal hypersensitivity may amplify the consequences of rapid gastric emptying. Doing so is necessary to better understand the pathogenesis of symptoms and devise therapies targeted to the underlying disturbance in DM.

Vagal neuropathy

Vagal dysfunction has been implicated as a mechanism for GI sensorimotor dysfunctions in DM¹⁴. The plasma pancreatic polypeptide (PP) response to sham feeding evaluates GI vagal function¹⁵. In clinical practice, assessment of cardiovascular vagal functions is used as a surrogate measure of GI vagal dysfunction. Only 1 study evaluated the relationship between cardiovascular and GI vagal dysfunction (i.e., gastric acid secretion, PP response to sham feeding) and observed a modest correlation¹⁵. The utility of the sham feeding response and cardiovascular measures to predict upper GI sensorimotor dysfunctions is unknown and will be evaluated in this study.

Small intestinal epithelial permeability and mucosal inflammation

A recent study suggests that patients with functional dyspepsia have low-grade mucosal inflammation, abnormalities of cell-to-cell adhesion proteins which predispose to increased epithelial permeability, and a leaky epithelial barrier¹⁶. Type 1 DM is associated with increased small intestinal permeability even in subjects who do not have celiac disease^{17,18}. Moreover, a comparison of 339 type 1 DM patients and 89 first degree relatives observed higher serum zonulin levels in type 1 DM patients than controls or relatives; patients with increased zonulin had increased epithelial permeability¹⁹. The only study which evaluated small intestinal permeability in type 2 DM used suboptimal techniques and reported normal permeability²⁰. However, a high fat diet induced glucose intolerance, decreased intestinal tight junction proteins, increased epithelial permeability, and plasma concentrations of circulating cytokines in OLETF mice, which is a

Small intestinal dysmotility, more frequently characterized by reduced than by increased motility²⁷, may also contribute to gastric stasis in DM. We recently observed increased sensitivity during duodenal carbohydrate and separately lipid perfusion in approximately 50% of patients with functional dyspepsia (Figure 1). Moreover, increased sensitivity was associated with higher plasma concentrations of GLP-1 during lipid infusion and more severe dyspeptic symptoms during daily life (unpublished data). Previous

spontaneous CCK-1 receptor knockout mouse and an animal model of obesity³². Given the similarities between this mouse model and type 2-DM in humans, it is conceivable that epithelial permeability is also increased in type 2 DM.

3 RESEARCH DESIGN AND METHODS

3.1 Study Design

In addition to questionnaires, the primary study procedures include assessment of:

- i) Screening visit – The participant will undergo a physical examination if one has not been completed within the last 3 months.
- ii) Study day 1 - GI vagal function by sham feeding, autonomic functions, small intestinal permeability test and enteral nutrient infusion of lipids, to be performed in that order, on another day (Charlton 7 CRU)
- iii) Study day 2 – Women of child bearing potential will have a urine pregnancy test within 48 hours before the GI Transit study, Gastric emptying of solids and liquids and small intestinal transit on 1 day (Charlton 7 CRU)
- iv) Study day 3 - Upper gastrointestinal endoscopy with a small amount of fluid and intestinal biopsies

These tests will preferably be performed in the order listed above. (ii) must always be performed before (iv). Ancillary procedures include collection of blood for genetic and epigenetic studies and a stool sample for microbial assessment. Vital signs and nurse assessment will be performed at each visit.

3.2 Study Subjects

We plan to accrue up to 115 subjects to ensure that 104 subjects complete the study in its entirety. 40 patients with DM and GI symptoms and 40 patients with functional dyspepsia will be recruited from the clinical practice; 24 healthy subjects will be recruited by public advertisement. To reduce the possibility of demographic differences between controls and patients, we will "frequency match" on age and gender by recruiting 5 controls after each set of 5 patients is studied. Doing so will provide similar age and gender distribution in each type. We will also attempt to recruit an even number of subjects with type 1 and 2 DM.

Inclusion criteria for controls

1. Healthy male or non-pregnant, non-breastfeeding female volunteers;
2. 18-70 years old;
3. Able to provide written informed consent before participating in the study;
4. Able to communicate adequately with the investigator and to comply with the requirements for the entire study

Additional inclusion criteria for patients

1. Symptoms of dyspepsia (i.e., early satiety, postprandial discomfort, nausea, vomiting, regurgitation)

2. Patients in the DM group will also require Type 1 or 2 DM of \geq 3 years duration; in patients with type 2 DM, the dyspepsia symptoms should have begun or worsened after DM was diagnosed

Exclusion criteria – for patients and controls

1. Major abdominal surgery (i.e., appendectomy, cholecystectomy, tubal ligation, hysterectomy, and limited colonic resection are permissible)
2. Clinical evidence (including physical exam and EKG) of significant cardiovascular, respiratory, renal, hepatic, gastrointestinal, hematological, neurological, psychiatric or other disease that may interfere with the objectives of the study and/or pose safety concerns
3. Opiates, alpha adrenergic agonists, metoclopramide, and high doses of anticholinergic agents (eg, amitriptyline greater than 50 mg daily). If medically safe, these drugs may be discontinued for four half lives prior to study assessments
4. Treatment with GLP-1 agonists and amlodipine which cause vagal blockade and may affect central processing of pain
5. Use of tobacco products within the past 1 week or NSAIDs or aspirin within the past week (since they all may affect intestinal permeability)
6. Bleeding or clotting disorders or medications that increase risk of bleeding from mucosal biopsies
7. Positive tissue transglutaminase antibodies (TTG),
8. For two days prior to studies, subjects will be instructed to avoid ingestion of artificial sweeteners such as SplendaTM (sucralose), NutrasweetTM (aspartame), foods containing lactulose or mannitol
9. Pregnant or breast-feeding females
10. Known intolerance or allergy to eggs
11. Poor peripheral venous access, if central venous access is not available
12. Any other condition or prior therapy that, in the opinion of the investigator, would make the patient unsuitable for the study

Exclusion criteria for controls only

1. Current symptoms of a functional gastrointestinal disorder assessed by questionnaire

Exclusion criteria for patients only

1. Severe vomiting that would preclude tube placement or participation in the study
2. Structural cause for symptoms by endoscopy within the past 48 months
3. Patients with gastric pacemakers

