3.5 Data Analysis

Chemosensitivity will be measured using a 100mmVAS anchored at each end (left end:No symptoms, right end: Severe symptoms). The distribution of this measure will be checked for its approximation to a gaussian distribution. An analysis to provide preliminary data for a new grant submission will be examined after approximately 15 subjects (5 DM, 10 controls) have completed the studies, but there is no intention of stopping the study based on the preliminary results. We anticipate conducting this analysis in July 2014 or thereafter.

Question	Summary Parameter	Statistical analysis
Sensation (symptoms) during enteral infusion (Aim 1)	VAS score	i) compare VAS scores in response to lipid infusion + exendin vs. lipid infusion + placebo separately for each group using a 2-sample t-test or Wilcoxon rank sum test ii) compare the delta VAS scores (exendin – placebo) to assess the association with subject status (FD,DM, and controls) using an ANOVA model (adjusting for covariates, eg, type of DM) or Kruskal-Wallis test.
Relationship between intestinal chemosensitivity and severity of ongoing upper GI symptoms	Mean symptom score and QoL defined by the Nepean dyspepsia index and GCSI diary	Multiple linear regression with the dependent variable = mean symptom score, and separately the QoL score (possibly after rank transformation). Potential predictor variables = VAS score during enteral lipid + placebo infusion, gastric emptying, age, gender, BMI
Relationship between sensation and plasma hormones during lipid infusion (Aim 2)	Using the VAS score from the enteral infusions and for hormones, the AUC values	Spearman correlations between the VAS score and the AUC values for the various hormones, overall and separately by group (FD,DM, controls)
Small intestinal tight junction proteins,	Protein expression, lactulose:mannitol	Assess the associations between permeability and protein expression, vs. the VAS score, based on Spearman

permeability, intestinal chemosensitivity	ratio, VAS score	correlations.
---	------------------	---------------

The sample size estimate is based on our previous study which evaluated intestinal chemosensitivity in functional dyspepsia in which the proportions with severe symptoms were assessed. [In the current proposal, symptoms during lipid infusion will be evaluated on a continuous VAS scale, likely providing the ability to detect smaller effect sizes]. The effect of lipid plus

Group	Proportions (%) with severe symptoms			

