	exendin+lipid vs. placebo+lipid	Controls vs. FD (exendin+lipid)	Controls vs. DM (exendin+lipid)	FD vs. DM (exendin+lipid)
Controls(n=12 vs n=12)	10% vs. 68%	10% vs. 60%	10% vs. 60%	30% vs. 73%
functional dyspepsia (n=20 vs. 20)	10% vs. 50%			
DM (n=20 vs. 20)	10% vs. 50%			

placebo vs. lipid plus exendin in response to enteral infusion can be based on a comparison of the proportions with severe symptoms using a two sample t-test. The association of group status with response to lipid plus exendin can also be assessed using a two-sample t-test for proportions. There is ~80% power (alpha =0.05, 2-sided) to detect the specified differences listed in the table below.

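### The 5-controls-per-5-patients matching rule cannot be carried out with 24 controls and 80 patients, and no analysis row names age or gender for the patient-versus-control comparison of VAS

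*Combined protocol and SAP*

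**What the plan says.** Section 3.2 of the combined protocol and SAP takes 40 DM and 40 FD patients from clinical practice, while "24 healthy subjects will be recruited by public advertisement". On the total it says: "We plan to accrue up to 115 subjects to ensure that 104 subjects complete the study in its entirety". The same paragraph sets a frequency-matching rule for age and gender, namely "recruiting 5 controls after each set of 5 patients is studied. Doing so will provide similar age and gender distribution in each type". It gives no other ratio, no age bands, and no rule for choosing the controls within a block.

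In Section 3.5, the first row of the analysis table has two parts. Part (i) is to "compare VAS scores in response to lipid infusion + exendin vs. lipid infusion + placebo separately for each group". Part (ii) relates a delta VAS (exendin minus placebo) to subject status, "using an ANOVA model (adjusting for covariates, eg, type of DM) or Kruskal-Wallis test". Age and gender appear in that table only in the symptom-severity regression, whose potential predictors are "VAS score during enteral lipid + placebo infusion, gastric emptying, age, gender, BMI". Outside the table, Section 3.4 lists them as potential covariates for the epigenetic work. The sample-size paragraph adds: "The association of group status with response to lipid plus exendin can also be assessed using a two-sample t-test for proportions".

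**The concern.** The matching rule is the plan's only stated protection against age and gender differences between advertised-for volunteers and clinic patients. If it cannot be followed, the protection has to come from a different matching ratio or from adjustment, and the plan commits to neither. Aim 1A, that DM patients with GI symptoms are more chemosensitive than controls, is a comparison of non-randomised groups. It is therefore the place where a difference in age or gender mix could be mistaken for a disease effect, and the same holds for controls versus FD.

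**Working it through.** **Planned numbers.** 40 + 40 + 24 = 104, which reproduces the stated number of completers. Spare accrual is 115 - 104 = 11, so controls can number at most 24 + 11 = 35.

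**What the rule needs** (controls = 5 x patients / 5):

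| Reading | Sets of 5 | Controls needed | Total subjects |
|---|---|---|---|
| All 80 patients | 16 | 80 | 160 |
| One patient group of 40 | 8 | 40 | 120 |

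Both totals exceed 115, and both control counts exceed 35. The planned ratio is 24/80 = 0.30, or 3 per 10, against 1.0 in the rule.

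**How far the rule would get if followed literally.** 24/5 = 4.8 sets, so the last controls come after about patient 25. That covers 25/80 = 31% of patients; 55/80 = 69% have no controls recruited after them. For one group of 40, 15/40 = 38% are left over. With all 11 spare places given to controls, 35/80 = 44% are covered. These figures count departures from the written sequence. They do not measure imbalance.

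**Size of a possible imbalance.** The documents do not allow it to be computed. Two markers, both resting on assumptions:

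- *Chance alone*, if controls and patients came from the same age distribution. The standard error of the difference in mean age, in SD units, is sqrt(1/24 + 1/80) = 0.23 against all patients, sqrt(1/24 + 1/40) = 0.26 against one group, and sqrt(1/12 + 1/20) = 0.37 for one infusion arm of controls against one arm of a patient group.
- *Illustrative bias.* Shift in an unadjusted contrast = correlation x age gap. With a gap of 0.25 to 0.5 SD and a correlation between age and VAS of 0.1 to 0.5, this runs from 0.1 x 0.25 = 0.025 SD to 0.5 x 0.5 = 0.25 SD. For 12 versus 20 (two-sided 0.05, 80% power) the detectable difference is 1.06 SD, so the shift is 0.025/1.06 = 2% to 0.25/1.06 = 24% of it.

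**Whether the analysis table covers the gap.** Part (i) compares infusions within a group, so it contains no patient-versus-control contrast. Part (ii) compares an exendin effect across groups. It leaves its covariate list open, but the one covariate it names, type of DM, is not defined for controls or FD patients, and Kruskal-Wallis takes no covariates. The sentence on group status in the sample-size paragraph is a basis for power, not a committed analysis. No row sets out control versus DM or control versus FD on VAS itself.

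**Why part (ii) cannot simply take extra covariates.** Subjects are randomised 1:1 to exendin or placebo (Abstract; Section 3.3, item v), and the power table uses 12 versus 12 and 20 versus 20. Nobody receives both, so no subject has a delta. Because the infusion is randomised within group, main effects of age and gender also cancel in expectation from each group's delta. A simulation with a 0.5 SD age gap and a slope of 0.5 gave a mean bias of 0.001 (simulation SE 0.004).

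**The case against.** The strongest reply is that frequency matching depends on whom the controls resemble, not on a 1:1 count. Twenty-four well-chosen controls can mirror the patients, Section 3.2 states that goal, and only the block size is wrong. This stands: if controls are chosen to mirror the patients studied and the patient mix is stable over accrual, the expected gap is zero.

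Nor should the run-out at patient 25 be read as a forecast. Section 3.5 plans a preliminary look at about 15 subjects, 5 with DM and 10 controls, so the investigators do not expect strict five-after-five accrual. This weakens the 31% and 69% figures as a description of what will happen. It does not supply a workable rule.

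A reader might also infer that the plan rules out adjustment for age and gender. It does not, since the covariates in part (ii) are introduced only by example. The narrower point remains: the plan thinks these two factors important enough to match on, yet does not name them where matching could fail.

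Finally, the missing Aim 1A row is a gap whether or not matching works. That is fair; it matters here because adjustment is the fallback when matching is incomplete.

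**Conclusion.** The point holds as a contradiction within one paragraph of Section 3.2. The 1:1 rule does not fit 24 controls on either reading of which patients it covers, nor within the cap of 115, so the assurance of similar age and gender distributions is unsupported. The arithmetic needs no assumptions.

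The consequence is limited. The control-versus-DM and control-versus-FD comparisons of VAS are open to age and gender differences that no analysis row is committed to handle. It would go too far to say that the groups will be imbalanced or that Aim 1A will be confounded: nothing in the documents shows a gap, and the 2% to 24% range rests wholly on assumed age gaps and correlations. It would also go too far to say that the exendin comparisons are compromised, since they are randomised within group, or that the sample size is wrong. The plan's 24 controls are the fixed number, and the matching rule has to be brought into line with them.

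**What to change.** 1. **Matching rule, Section 3.2.** Use a ratio that fits the planned numbers, for example 3 controls after every 10 patients (8 x 3 = 24, 8 x 10 = 80). Three controls cannot fill an age-by-gender grid in each block, so choose them cumulatively to reflect the mix of DM and FD patients accrued so far. Say that this *is intended to provide* similar distributions. Controls matched to the pooled patients need not match DM or FD separately, so matching should not stand alone.
2. **New row, Section 3.5.** Add control versus DM (Aim 1A) and control versus FD on VAS by linear regression/ANCOVA with age and gender as covariates, stating which infusion arm or arms are used. The plan already says of VAS: "The distribution of this measure will be checked for its approximation to a gaussian distribution". If that check fails, run the same model on ranks, which keeps the adjustment.
3. **Delta-VAS part of the first row.** Recast it as a group-by-treatment interaction in a model of VAS. Age and gender can enter this model, mainly for precision.

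**Cost.** No extra subjects or measurements; control accrual is spread over a longer period. For 12 versus 20, residual degrees of freedom fall from 30 to 28 and the critical t rises from 2.042 to 2.048. If the covariates explain none of the outcome, the variance of the contrast is multiplied on average by the ratio below. The first ratio equals 29/27; all three were simulated with a Normal age and a 50:50 gender indicator. Break-even is 1 - 1/ratio.

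| Difference in mean age | Variance ratio | Rise in standard error | Break-even share of within-group VAS variance |
|---|---|---|---|
| 0 SD | 1.074 | 3.6% | 6.9% |
| 0.5 SD | 1.145 | 7.0% | 12.7% |
| 1 SD | 1.351 | 16% | 26.0% |

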Hence, we propose to evaluate the overall hypothesis that intestinal chemosensitivity related to increased epithelial permeability and GLP-1 explains symptom severity in patients with functional dyspepsia and in patients with DM and dyspepsia. 24 healthy subjects, 40 patients with DM and GI symptoms, and 40 patients with functional dyspepsia will undergo assessment of intestinal chemosensitivity during duodenal nutrient perfusion, gastric emptying (by scintigraphy), cardiovascular and GI vagal functions (plasma pancreatic polypeptide response to sham feeding and a comprehensive autonomic reflex screen), in vivo assessment of small intestinal permeability (urinary lactulose:mannitol ratio), and upper endoscopy with assessment of epithelial tight junction proteins and permeability on small bowel biopsies. During the nutrient infusion, subjects in each group (ie, healthy subjects, functional dyspepsia and DM) will be randomized to lipid infusion and placebo or lipid infusion {66.7 mL Microlipid (0.5 gm/mL diluted in water to 222 mL)} and exendin 9-39 in the ratio of 1:1. Hormonal responses (i.e., GLP-1, CCK, GIP, glucagon, PYY, C-peptide, and insulin) and plasma glucose will also be evaluated during enteral nutrient infusion. GI symptoms during each perturbation (meal, nutrient infusion) will be evaluated by validated questionnaires. Blood will be collected for DNA-based genetic analyses, initially to assess the relationship of GI sensorimotor dysfunctions and symptoms with SNPs affecting CCK and GLP-1 receptors. The analysis will assess for disturbances in these parameters in functional and DM dyspepsia, investigate associations between symptoms during enteral infusion and hormonal-epithelial functions, and evaluate relationships between daily symptoms and results of testing.

Table of Contents

ABSTRACT.....	1
1 SPECIFIC AIMS	3
2 BACKGROUND AND SIGNIFICANCE.....	5
3 RESEARCH DESIGN AND METHODS.....	7
3.1 Study Design.....	7
3.2 Study Subjects.....	7
3.3 Details of Study Assessments	8
3.4 Gene and Epigenetic Studies	15
3.5 Data Analysis	16
3.6 Potential Pitfalls.....	17
4 HUMAN SUBJECTS	17
5 SAFETY AND ADVERSE EVENTS	19
5.1 Definitions.....	19
5.2 Recording of Adverse Events	21
5.3 Reporting of Serious Adverse Events and Unanticipated Problems.....	22
5.3.1 Sponsor-Investigator reporting: notifying the Mayo IRB.....	22
5.3.2 Sponsor-Investigator reporting: Notifying the FDA.....	22
5.4 Stopping Rules	23
5.5. Medical Monitoring	23
APPENDIX.....	23

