v) Hormonal responses and symptoms during duodenal infusions. A small bore nasogastric tube will be inserted through the nostril into the stomach over a guidewire and advanced under fluoroscopic guidance until the infusion ports are in the 2nd part of the duodenum.

Thereafter, subjects in each group (ie, functional dyspepsia and DM) will be randomized to lipid infusion {66.7 mL Microlipid (0.5 gm/mL diluted in water to 222 ml)} together with placebo or exendin 9-39 in the ratio of 1:1. Lipids will be delivered into the duodenum at an infusion rate which matches the rate at which glucose enters the systemic circulation after oral glucose. After placement of an IV in the hand or forearm vein for blood draws, this hand will be placed in a hotbox heated to 55°C. We have considerable preliminary data for symptoms and hormonal responses with this paradigm. Plasma glucose, insulin, C-peptide, GLP-1, CCK, ghrelin, and PYY will be collected at 5 minute intervals for 30 minutes, 10 minute intervals from 30 – 60 minutes, and at 15 minute intervals from 60 – 180 minutes (18 times including 0 minutes).

vi) GLP-1 antagonist exendin 9-39 will be sourced from C.S. Bio, reconstituted in the Mayo Pharmacy by an established process used in previous studies, and undergo endotoxin testing, sterility testing and bacterial testing, and held in quarantine before it will be used in humans. Research compounded sterile preparations (CSP) are prepared and assessed for end preparation testing according to USP <797> in the hospital pharmacy services production lab. Each batch is tested for sterility according to USP <71> utilizing membrane filtration. The sterility testing is validated by a formulation Bacteriostasis Fungistasis test. The amount of each batch tested is determined by USP <71>. Each batch is tested for endotoxin according to USP <85>. High risk CSP are quarantined for 14 days and when all end preparation testing is completed.

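### Diabetes type is a planned covariate only in the three-group ANOVA; the DM-only exendin comparison, where it would help most, is unadjusted, and no stratification by type is stated

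*Combined protocol and SAP*

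**What the plan says.** **Recruitment.** Section 3.2 sets the DM group at 40 patients and admits both types ("Patients in the DM group will also require Type 1 or 2 DM of" at least 3 years' duration). It then adds: "We will also attempt to recruit an even number of subjects with type 1 and 2 DM".

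**Randomisation.** The Abstract says that "subjects in each group (ie, healthy subjects, functional dyspepsia and DM) will be randomized to lipid infusion and placebo or lipid infusion" plus exendin 9-39. Section 3.3 v) repeats the rule by group, "together with placebo or exendin 9-39 in the ratio of 1:1". Neither place mentions DM type, blocking or any stratification factor beyond the subject group.

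**Analysis.** The first row of the Section 3.5 table has two parts.
- Part (i) compares VAS scores on exendin and on placebo separately in each group, by a two-sample t-test or a Wilcoxon rank sum test. No covariate is named.
- Part (ii) compares the exendin-minus-placebo difference across FD, DM and controls "using an ANOVA model (adjusting for covariates, eg, type of DM) or Kruskal-Wallis test".

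Part (ii) is the only place in the analysis plan that names DM type. It is not among the regression predictors in Section 3.5 or the epigenetic covariates in Section 3.4.

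**The concern.** The plan treats DM type as worth balancing at recruitment and worth adjusting for in analysis, but it puts the adjustment in the less useful of two places.

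In the three-group ANOVA, FD patients and controls have no DM type. The term can only split the DM group into type 1 and type 2. The plan does not say how it would be coded, and the Kruskal-Wallis alternative takes no covariate at all.

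In the DM-only drug comparison every patient has a DM type, and an ordinary additive adjustment would work. That comparison is unadjusted. With 20 patients per arm and no stated stratification, the arms can differ noticeably in their mix of types. If VAS scores during lipid infusion differ by type, the drug contrast carries that extra noise.

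The documents give one reason to expect a difference. The overall hypothesis ties chemosensitivity to epithelial permeability, and Section 2 reports raised permeability in type 1 DM, while the one type 2 study, described as technically suboptimal, found it normal. No VAS data by type are given.

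**Working it through.** **1. The plan's own figure.** The DM row in Section 3.5 has 20 vs 20, 10% vs 50% with severe symptoms, two-sided alpha 0.05, and power of about 80%.
- Pooled proportion: (0.10 + 0.50)/2 = 0.30.
- Null SE: √(0.30 × 0.70 × 2/20) = √0.021 = 0.1449.
- Alternative SE: √(0.10 × 0.90/20 + 0.50 × 0.50/20) = √0.017 = 0.1304.
- Power: Φ[(0.40 − 1.96 × 0.1449)/0.1304] = Φ(0.89) = 81.3%.

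The figure reproduces. DM type does not enter it, so this point leaves it unchanged.

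**2. Chance imbalance.** Assume exactly 20 type 1 and 20 type 2 patients, allocated 20:20 without regard to type. Let X be the number of type 1 patients on exendin. Then P(X = k) = C(20,k)²/C(40,20).
- P(10) = 0.2476; P(9) = P(11) = 0.2047; P(8) = P(12) = 0.1151; P(7) = P(13) = 0.0436.
- 12:8 or worse: 1 − 0.2476 − 2 × 0.2047 = 0.343.
- 13:7 or worse: 0.343 − 2 × 0.1151 = 0.113.
- 14:6 or worse: 0.113 − 2 × 0.0436 = 0.026.

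**3. Effect on the unadjusted contrast.** Let D be the type 1 minus type 2 difference in mean VAS. With X type 1 patients on exendin and 20 − X on placebo, the contrast shifts by D × (2X − 20)/20: 0.20 D at 12:8, 0.30 D at 13:7, 0.40 D at 14:6.

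The documents do not give D, so I show a range in units of the overall SD. The SE of a 20 vs 20 difference is √(2/20) = 0.316 SD.

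| Assumed D | Shift at 12:8 | Shift at 13:7 | SE unadjusted | SE adjusted for type, 10:10 split |
|---|---|---|---|---|
| 0.5 SD | 0.10 SD | 0.15 SD | 0.316 SD | 0.316 × √(1 − 0.5²/4) = 0.306 SD |
| 1 SD | 0.20 SD | 0.30 SD | 0.316 SD | 0.316 × √(1 − 1²/4) = 0.274 SD |

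The last column uses the fact that, with equal numbers of each type, type accounts for D²/4 of the variance. Adjustment therefore cuts the SE by about 3% at D = 0.5 SD and 13% at D = 1 SD. All the shifts shown are smaller than one SE.

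**4. What stratification adds to adjustment.** The correlation between arm and type is 0.2 at 12:8, from (12 × 12 − 8 × 8)/(20 × 20), and 0.3 at 13:7. The adjusted SE is inflated by 1/√(1 − 0.2²) = 1.02 and 1/√(1 − 0.3²) = 1.05. Adjustment brings most of the gain; stratification saves a further 2% to 5% when the split is that uneven.

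**5. Type in the three-group model.** Take an intercept, dummies for FD and DM, and dummies for type 1 and type 2. The DM column equals type 1 plus type 2, so the five columns have rank 4. Dropping the redundant column leaves a four-level factor: control, FD, type 1, type 2. Type is estimable there, but only as a contrast within DM.

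**The case against.** **Randomisation already protects the comparison.** This stands. Without stratification the DM exendin contrast is unbiased over repeated allocation, and variation due to type sits in the within-arm variance, so the t-test and its interval allow for chance imbalance. A reader might infer that the exendin effect would be confounded with DM type. The documents do not support that: the cost is precision, plus an avoidable shift in whatever allocation is realised.

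**Type can be used in the ANOVA.** This stands too. A reader might infer that DM type is undefined there and cannot act as a covariate. Step 5 shows that it can, once coded as nested. What is missing is the coding, in a table entry where type is offered only as an example.

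**Type does not fix insulin handling.** A reader might infer that type determines insulin use during the infusion, so that imbalance in one is imbalance in the other. Section 3.3 ties insulin to whether the patient is treated with it: insulin-treated type 2 patients are handled like type 1, and only type 2 patients not on insulin differ. Stratifying by type would not guarantee balance in insulin use, and I do not rely on it.

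**Silence is not exclusion.** The plan gives groups and a ratio and says nothing of how the sequence is generated. Stratification by type is unstated, not ruled out.

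**The ANOVA has a larger difficulty.** Its response is an exendin-minus-placebo difference, which no single subject has when each is randomised to one arm. Recoding type does not repair that; it is a separate matter.

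**Conclusion.** The point holds as a minor one. The plan names DM type only in the model where it is nested in one level of the group factor, and leaves it out of the DM-only drug comparison, where it would directly reduce the SE.

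The size depends on the type 1 versus type 2 difference in VAS, which the documents do not give. At assumed differences of 0.5 to 1 SD, adjustment narrows the SE by about 3% to 13%. A 12:8 or worse split has a 34% chance and a 13:7 or worse split 11%, with unadjusted shifts of 0.2 and 0.3 times the difference at those splits. If there is no difference by type, nothing is gained and one degree of freedom is spent.

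These figures assume that the 20:20 split by type is achieved, which Section 3.2 only undertakes to attempt, and that allocation is not in fact stratified. Neither the validity of the DM comparison nor the stated power is in question.

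**What to change.** 1. **DM-only comparison.** Replace the unadjusted test with a linear model for VAS containing treatment and DM type as main effects. If the distribution is far from Gaussian, use a rank test stratified by type (van Elteren). This can be done at any time before the data are analysed, even if enrolment is complete.
2. **Randomisation.** State whether DM allocation is stratified by type. If it is not, stratify any allocation still to be made, using short blocks because each stratum has only about 20 patients.
3. **Three-group model.** Wherever type is used, specify it as nested within DM, or equivalently use the four-level factor (control, FD, type 1, type 2).

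**Cost.** One model term (one degree of freedom) and one extra randomisation list. No change in sample size is needed.
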